6. DOCUMENTATION OF STATISTICAL METHODS

6.1 General Remarks

6.1.1 *Missing and Partially Known Dates*

Missing dates will not be replaced. Unless specified otherwise, partially known dates will be defined as follows for duration computation:

- Partially known begin date:
 - If only the day is missing, it is estimated as the first day of the month or the day of the inclusion date (if the month of the inclusion date is the same as the month of the begin date).
 - If month and day are missing, they are estimated as January 1 or the month and day of the inclusion date (if the month and day of the inclusion date are the same as the month and day of the begin date).
- Partially known end date:
 - If only the day is missing, it is estimated as the last day of the month or the day of the last visit date (if the month of the last visit date is the same as the month of the end date).
 - If month and day are missing, they are estimated as December 31 or the month and day of the last visit date (if the month and day of the last visit date are the same as the month and day of the end date).

Partially known dates and duration calculations with day/month imputations will be presented during the data review meeting for reviewed in a blinded manner.

6.2 Demographics

The following rules will be applied for the computation of age and BMI:

- **Age** will be calculated in years using the following formula: $\text{age} = (\text{initial visit date} - \text{birth date}) / 365.25$. Date of initial visit will be taken at inclusion visit (Visit 1). Results will be expressed with two decimals.
- **BMI** will be calculated in kg/m^2 using the following formula: $[\text{Last known weight (Kg)} / \text{Height (cm)} * \text{Height (cm)}] * 10000$. Results will be expressed with two decimals.

6.3 Durations

The following durations will be computed for the analyses:

- **Duration of delivery** will be defined in hours as: end date/time of delivery – start date/time of delivery.
- **Duration since start of delivery until start of previous/concomitant treatment administration** will be defined in hours as: start date/time of treatment administration – start date/time of delivery.
- **Follow-up duration in the study** will be defined in days as: hospital discharge or premature withdrawal date – date of V1.
- **Duration of haemorrhage** will be defined in hours as: end date/time of haemorrhage – start date/time of haemorrhage.
- **Duration since H0 before haemostatic intervention** will be defined in hours as: date/time of haemostatic intervention – start date/time of study treatment administration (H0).

6.4 Previous and Concomitant Treatments

Descriptive statistics for treatments collected on an ongoing basis during the study and coded with the WHO Drug dictionary will be presented by treatment group according to the pharmacological class of the ATC classification system (four first letters of ATC code) and the drug generic name (preferred name).

Previous and concomitant treatments will be distinguished as follows:

- A **previous treatment** is a treatment, whether ongoing or not, which was started before the start of IMP administration: treatment start date/time < study treatment administration start date/time (H0).
- A **concomitant treatment** is a treatment which started after the start of IMP administration: treatment start date/time ≥ study treatment administration start date/time (H0).

6.5 Adverse Events

All Aes will be categorised as emergent (TEAEs) or not emergent as follows:

- **Not emergent:** start date/time before the start date/time of IMP perfusion (H0) or after the date of hospital discharge (Visit 6).
- **Emergent:** start date/time on or after the start date/time of IMP perfusion (H0) and on or before the date of hospital discharge (Visit 6).

The period between the start date/time of IMP perfusion (H0) and the date of hospital discharge is retained for the definition of an emergent AE as it is expected to cover the duration of Clottafact[®] exposure (including elimination half-life).

If start and/or end dates/times of an AE are missing, partially missing or unknown, the AE will be considered as emergent.

The **duration of the AE** will be computed in days as the difference between the end and start dates/times using the following formula: AE end date/time – start date/time + 1.

Treatment-related Aes are those described by the investigator as possibly related to study treatment or as Aes with unknown relationship.

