9.5.8. Follow-up of Adverse Events

During the study:

All AEs and SAEs must be followed-up during the study period until resolution or stabilisation.

After the end of the study, or at patient's premature discontinuation:

Only AEs or SAEs related to the study IMP that occurred during the study and:

- That are still recorded as “recovering”, “not recovered” or “worsening” at the end of the study, must be continuously followed-up as part of the study data, as long as necessary to adequately evaluate the patient’s safety, or until they are considered as “resolved”, or until the condition is stabilised, or until the Investigator no longer estimates that they are clinically significant. If resolved, a resolution date must be provided.

If a patient is withdrawn from the study due to safety reasons, she should be followed until the event disappears, is otherwise explained or the patient’s condition has stabilised.

Any patient who voluntarily withdraws from the study should be carefully questioned for the possible occurrence of an adverse event.

If no follow-up information can be provided, the Investigator must:

- Provide a written justification and
- Document the outcome as “unknown” (except for cases where the outcome is known, such as death for instance)

(Reminder: if the Investigator detects a new (S)AE after the end of the study and considers the event as possibly related to the IMP, he/she has to contact the Sponsor to determine how it should be documented and reported.)

Follow-up documentation

- In case of follow-up of an AE that worsened in nature or in severity, the follow-up will be documented on a new AE column in the CRF, with the box "follow-up" being ticked

- In case of follow-up of an SAE for which additional information/modification is provided, the follow-up will be reported on a new “SERIOUS ADVERSE EVENT FORM”, with the box "follow-up" being ticked

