12.11. Safety Analysis

Analyses of safety endpoints will be conducted in the safety set. Missing data will not be replaced.

With respect to AEs, all AEs occurring during the treatment period will be classified using the Lowest Level Term (LLT), Preferred Terms (PT) and System Organ Class (SOC). The duration of the AE and the duration between the last dose of IMP and onset of the adverse event will be calculated.

The number of patients with at least one AE will be tabulated by treatment group, SOC, PT and LLT. Patients with SAEs, IMP-related AEs and other significant AEs will be tabulated by treatment group, SOC, PT and LLT.

The number of AEs will be tabulated by treatment group, SOC, PT and LLT.

All SAEs, IMP-related AEs and other significant AEs will be listed by treatment group, SOC, PT and LLT.

The standard dictionary for coding events will be the MedDRA (version 16.0).

AEs reported before the start of IMP infusion will only be listed with individual patient's AE data collected, if applicable.

Raw laboratory variables (including baseline data) will be presented by treatment group at each determination (H0, H6 and D2) and shift tables will also be displayed at the same periods. Determinations at other sampling times will be listed except if other specific times are defined in the SAP.

Arterial and venous thromboembolic events over the study period will be compared between treatment groups by chi-square.

No statistical tests will be performed on other variables except if it is needed to explore any AE with possible clinical significance.

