4. SAFETY EVALUATION

Analyses of safety endpoints will be conducted in the safety set (SS).

Missing data will not be replaced.

The standard dictionary for coding adverse events will be the MedDRA (version 17.1).

All AEs will be classified as emergent (i.e. happening or worsening after the time of start of IMP perfusion, defined as treatment-emergent adverse event, TEAEs) or not emergent.

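### SAP 6.5 makes an adverse event treatment-emergent when only its end date/time is missing, even if its known onset lies outside the emergent window; SAP 4 and 6.5 should share one definition

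*SAP*

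**What the plan says.** SAP 4 calls an AE emergent when it is "happening or worsening after the time of start of IMP perfusion, defined as treatment-emergent adverse event, TEAEs". It states no end of window.

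SAP 6.5 gives the derivation. Emergent means "start date/time on or after the start date/time of IMP perfusion (H0) and on or before the date of hospital discharge (Visit 6". An onset before H0 or after discharge is not emergent, and worsening is not mentioned. The section gives a reason for ending at discharge: the period was retained "as it is expected to cover the duration of Clottafact" exposure, elimination included. It then adds a rule for incomplete dates: "If start and/or end dates/times of an AE are missing, partially missing or unknown, the AE will be considered as emergent".

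Protocol 12.11 says that "all AEs occurring during the treatment period will be classified using the Lowest Level Term", and that "AEs reported before the start of IMP infusion will only be listed". Protocol 9.5.4 collects AEs from consent to the end-of-study contact, 6 ± 2 weeks after delivery. Protocol 9.5.8 says "All AEs and SAEs must be followed-up during the study period until resolution or stabilisation", and for an AE that worsens, "the follow-up will be documented on a new AE column in the CRF".

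**The concern.** Whether an AE is treatment-emergent depends on when it began or worsened. Letting a missing end date decide the flag brings in something irrelevant and overrides a known onset. Two AEs with the same onset three weeks after discharge, one with an end date and one without, are classed differently under 6.5.

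End dates can be absent without any data error. Protocol 9.5.8 lets follow-up stop at stabilisation, and after the study it continues only for AEs related to the study product. An unrelated AE still present at the last contact may therefore never receive an end date. Protocol 11.1.2.4 provides a code for unknown items.

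Separately, the SAP defines the same flag in two places with different wording. What is at stake is whether the treatment-emergent tables can be reproduced from the text and mean what their titles say.

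**Working it through.** No sample size or error rate is involved. The check applies each rule as written to every combination of known onset (before H0, from H0 to discharge, after discharge) and end date/time (complete or missing), for an AE that does not worsen. That gives 3 × 2 = 6 cases.

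| Known onset | End date/time | SAP 4 | SAP 6.5, onset rule | SAP 6.5, after the missing-date sentence |
|---|---|---|---|---|
| Before H0 | complete | not emergent | not emergent | not emergent |
| Before H0 | missing | not emergent | not emergent | **emergent** |
| H0 to discharge | complete | emergent | emergent | emergent |
| H0 to discharge | missing | emergent | emergent | emergent |
| After discharge | complete | emergent | not emergent | not emergent |
| After discharge | missing | emergent | not emergent | **emergent** |

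**Within 6.5.** The onset rule and the missing-date sentence disagree in the two cases in bold. The section writes no exception for a known onset.

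**SAP 4 against 6.5 as finally applied.** They differ in two cases: onset before H0 with the end missing, and onset after discharge with complete dates. These counts describe combinations of rules. They are not shares of events.

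**Worsening.** Take an AE that starts before H0 and worsens afterwards, with complete dates. SAP 4 makes it emergent. Under 6.5 the answer depends on whether the new CRF column has its own start date and whether the flag uses it. The documents say neither.

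**Partial start dates.** Protocol 9.5.5 asks for dates of onset and resolution and does not mention times. A start recorded as a date without a clock time could count as partially missing. The literal rule would then make the AE emergent even if the date alone placed it weeks after discharge.

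**Where such events could come from.** Before H0 the interval is short: it runs from emergency consent to H0, and infusion is to start within 30 minutes of the start of prostaglandin. After discharge, collection runs to 6 ± 2 weeks after delivery, that is (6 − 2) × 7 = 28 to (6 + 2) × 7 = 56 days.

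**What uses the flag.** In the list of tables in SAP 5.2, 14.3.4.1 to 14.3.4.5 use it, which is five of the ten AE tables by treatment group. Tables 14.3.3.1 to 14.3.3.5 cover all AEs. Listings 14.3.5.1 to 14.3.5.4 select related AEs, AEs leading to discontinuation, SAEs and deaths. The thromboembolic comparison in SAP 4.2 covers the study period.

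**The case against.** The strongest reply is that SAP 4 is a summary line and 6.5 is the working derivation, so there is one rule and at most a missing cross-reference. For the window this largely stands. Section 6.5 gives a reason for discharge, and protocol 12.11 also speaks of a treatment period. A reader might infer that the discharge cut-off is itself an error, or that the SAP holds two rival windows. The documents do not support that. The cut-off is a stated choice, and SAP 4 simply fails to repeat it.

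On worsening, the new CRF column may carry its own onset date, in which case an onset rule would capture it. That is possible, but the SAP should say so.

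On end dates, an ongoing AE might be coded as not applicable and not treated as missing, which would narrow the trigger. Protocol 9.5.8 also requires a resolution date for AEs related to the study product that resolve after the study. This reduces the number of cases, but a date recorded as unknown still meets the wording.

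Defaulting to emergent is a cautious choice, and it applies alike to both blinded arms. It is sound when onset is unknown, and the fix keeps it. It has no basis when onset is known. Partially known dates also go to a blinded data review (SAP 6.1.1), but that provision concerns durations and does not settle classification.

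A reader might also see in the pre-H0 case a specific breach of protocol 12.11, under which such events are only listed. SAP 4.1 and 4.2 already tabulate all AEs, whatever 6.5 says, so that difference does not come from the missing-date sentence.

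**Conclusion.** The point holds, as a minor one. As written, 6.5 flags some AEs as emergent against its own onset rule because an unrelated field is missing, and leaves out otherwise identical AEs with complete dates. The difference in wording between SAP 4 and 6.5 is secondary: 6.5 is best read as the operational rule for the window, and worsening is left unspecified.

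The effect is limited to five descriptive tables. A reader might infer that late safety events are lost or that the comparison between arms is biased. The documents do not support either. The all-AE tables include every AE in the safety set whether or not it is flagged, and the planned comparison of thromboembolic events does not use the flag. The four listings do not depend on the flag either, but they are selective and should not be taken as a complete record.

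The number of events affected, and any difference between arms, cannot be computed from the documents. It is probably small, because the period before H0 is short and a post-discharge AE is wrongly flagged only if its dates are also incomplete. The conclusion rests on reading the missing-date sentence literally. How ongoing AEs are coded would change how often it applies, but would not remove the contradiction.

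**What to change.** In SAP 6.5, delete the words *and/or end* and replace the sentence with a rule such as:

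- An AE with a known onset is classed by that onset, whatever its end date/time (ongoing, unknown or not applicable included).
- If the start date/time is missing or partial, the AE is emergent unless the known part places onset before H0 or after the end of the window.

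Use the same definition in SAP 4, with the discharge cut-off written there if it is kept. If worsening stays in the definition, state in 6.5 that a worsening is classed by the date in its new CRF column, and give a default for a column with no date.

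The cost is a few lines in two SAP sections and one flag in the AE program, with no new data. The one extra task is to check the dates in the worsening columns before the flag is programmed.

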6.6 Laboratory Data

Haematology, biochemistry and coagulation test laboratory parameters and corresponding units are listed below.

- Haematology parameters:

Parameter	Unit
Hb	g/dL
Red cell	Count/L
Ht	%
Leucocyte	/mm ³
Platelets	10 ⁹ /L

- Biochemistry parameters:

Parameter	Unit
Urea	mmol/L
Creatinine	μmol/L

- Coagulation tests

Parameter	Unit
Prothrombin	%
Activated thromboplastin time ratio	-
D-Dimer	ng/mL
Factor II	%
Factor V	%
Fibrin monomer	μg/mL

The activated thromboplastin time ratio will be computed as the ratio between activated thromboplastin time “patient” (sec) and activated thromboplastin time “control” (sec).

6.7 Vital Signs

Vital sign parameters and corresponding units are listed below.

Parameter	Unit
Systolic blood pressure	mmHg
Diastolic blood pressure	mmHg
Heart rate	Beats/minute
Peripheral oxygen saturation	%

7. SAS CODE

7.1 SAS code fragments for primary analysis of the primary endpoint

The SAS code for the primary model is written as follows:

```

/*****
/* EURAXI PHARMA - SAS version 9.4 Programme created by [name] */
/* Date: 26/10/2018 Last modifications: */
/* Risk level : I Ib */
/* */
/* PROGRAM : F:\Data-Management\01 - Etudes\1016 - Fidel\11 -
Stat\Programmes\1016_FIDEL_EFFICACY_I.sas */
/* */
/* MACRO: %detect, %Stat_des */
/* */
/* Description : PRIMARY ANALYSIS (logistic model) */
/*****

ods graphics on;

ods output ParameterEstimates =_est OddsRatios =_or;
proc logistic data = Main_analysis descending;
class _trt centre _b_fibrinogen(PARAM=REF REF="> 4 g/L") / param=glm;
model _resp = _trt centre _b_fibrinogen /influence iplots;
run;
ods graphics off;

```

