8.2.2. Visit 2: Randomisation and IMP infusion

- Randomisation will be performed as soon as possible after inclusion and after the start of prostaglandins infusion (see Section 8.1.3).
- IMP administration
 - A third party reconstitutes the IMP (see [Section 6.4.2](#)).
 - The start of IMP infusion corresponds to H0 and should be within the 30 minutes following the start of prostaglandins infusion.
 - The start and the end times and the administered volume will be collected in the CRF.
- Concomitant treatments including intravenous fluids and blood products;
- Local tolerance which occurred during IMP infusion and AEs if any.

8.2.3. Visit 3: H2 (120 ± 30 min) / Blood sampling 2

The following data will be collected in the CRF:

- Blood sampling:
 - Complete blood count, Hb, Ht, platelets,
 - Haemostatic profile: fibrinogen, PT, QT, aPTT, D-dimers,
- Vital signs
 - Measurement of arterial blood pressure (systolic and diastolic),
 - Heart rate;
- Haemorrhage parameters:
 - Measured or estimated volume of blood loss from the start of bleeding;
- Concomitant treatments including intravenous fluids, blood products, tranexamic acid and fibrinogen concentrate as rescue therapy: any modification or institution of a new treatment;
- AEs if any.

8.2.4. Visit 4: H6 (360 ± 30 mn) / Blood sampling 3

[figure not shown]
The following data will be collected in the CRF:

- Blood sampling:
 - Complete blood count, Hb, Ht, platelets,
 - Haemostatic profile: fibrinogen, PT, QT, aPTT, D-dimers,
- Vital signs
 - Measurement of arterial blood pressure (systolic and diastolic);
 - Heart rate;
- Haemorrhage parameters:
 - Measured or estimated volume of blood loss from the start of bleeding;
- Concomitant treatments including intravenous fluids, blood products, tranexamic acid and fibrinogen concentrate as rescue therapy: any modification or institution of a new treatment;
- AEs if any.

8.2.5. Visit 5: morning of D2 / Blood sampling 4

Depending on the time of delivery, the assessment in the morning of D2 may differ from H48 (considering that the first blood sampling in hospital is performed around 7h00 in the morning).

H0 = start of IMP administration

Even if the patient has been transferred to another hospital or department within the same hospital, the investigator must ensure that all laboratory analyses will be performed, and the following parameters will be recorded in the CRF:

- Blood sampling:
 - Complete blood count, Hb, Ht, platelets,

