- Single or multi-organ failure (SOFA score) in women transferred to resuscitation and/or intensive care and/or PICU and/or continuous care units.
- Death during the study.

1.10.2.5 *Biological effects of fibrinogen concentrate administration*

- Change in plasma fibrinogen level between H0 (start if IMP infusion) and D2;
- Evolution of hemoconcentration between H0 and D2
 - Change in Hb level between each determination and H0
 - Change in Ht level between each determination and H0
 - Change in RBCs count between each determination and H0

1.10.2.6 *Tolerance of fibrinogen concentrate administration*

- Serious and non-serious adverse events (AE).

1.11 **SAMPLE SIZE CALCULATION**

It has been estimated that, in the control group, 42% of patients will fulfil the primary endpoint (unpublished data from the Pithagore cohort). With an expected percentage of patients in the Clottafact[®] treated group of 27%, the difference between the two groups will be 15%. With a power (1- β) of 90%, a type I error (α) of 5% and a two-

sided test (Z test, unpooled variance), a sample size of 206 patients is needed per treatment group. The rate of drop-out is assumed to be approximately 5%.

Therefore, 434 patients will be included in the study.

As there is some uncertainty about the test Z variance depending itself on the expected rates, the variance is re-estimated in a blind way at 80% of the initially planned sample size (i.e. 80% of 412=326 evaluable patients or 348 patients with adjustment for a 5% dropout rate) to maintain the power to 90% while still considering the same originally planned difference in failure rates, i.e. 15%. Given an estimated overall rate of failures higher than expected, the sample size was re-estimated at 470 patients to maintain the power to 90%. The recruitment period ended on June 30th, 2018 with 448 patients at this date. Based on this sample size of 448, and assuming that 1.55% of patients excluded from the ITT analysis (i.e. patients without receiving at least a dose of the IMP) the current power of the trial is 89.6%, which remains very close to the targeted power of 90%.

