3.3.5.3 Baseline Efficacy Variables

All efficacy variables will be presented by randomisation group. Baseline data are defined as the last available data before the start of IMP infusion.

Date and time of the last available Hb (g/dL) determination will be presented. The month of last recorded Hb value during pregnancy will be mentioned.

Fibrinogen, Hb, Ht and RBCs count will be displayed in the efficacy analysis section in order to display baseline and follow-up results in the same tables.

Exploratory variables are efficacy laboratory data and will be displayed in the efficacy analysis section.

3.3.5.4 *Baseline Safety Variables*

All safety variables will be presented by study treatment group. Baseline data are defined as the last available data before the start of IMP infusion.

All laboratory data except those defined as efficacy variables (in the above section) or as exploratory variables will be defined as safety criteria. All laboratory data will not be displayed in the baseline section but in the analysis of safety in order to display in the same table the baseline and other data.

3.3.5.5 *Investigational Product (IMP) and Concomitant Treatments*

3.3.5.5.1 *Extent of Exposure*

Summary tables will display the number of patients exposed, duration of exposure (in minutes, automatically derived from the start and end times of IMP infusion), in each randomisation group and, if applicable (any error in allocation treatment), in each treatment group.

3.3.5.5.2 *Treatment Compliance*

The delay between the start of prostaglandin infusion and the start of IMP infusion (in minutes) will be presented as a continuous variable.

The same variables will be estimated and presented on the “as treated” set (SS set) in each treatment group.

3.3.5.5.3 *Concomitant Treatment*

Concomitant treatments will be coded using the WHO DDE March 1, 2014 version.

The number and percentage of patients with at least one concomitant medication will be summarised by group. Concomitant medications will be described on SS set by anatomical therapeutic chemical (ATC) name, overall and by group.

3.3.6 *Efficacy analyses*

3.3.6.1 *Primary Efficacy Variable(s) and prognostic factors*

3.3.6.1.1 *Description of the primary efficacy variable(s)*

The primary efficacy variable is a binary composite endpoint (failure versus success). Failure is defined when a patient

- loses at least 4 g/dL of Hb compared to the reference Hb level,

and/or

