3.3.6.2.2 Model of analysis of the primary endpoint

The primary model of analysis will be a logistic regression to assess the association between a binary exposure variable treatment (variable “_trt”) and the binary outcome (variable “_resp”), adjusting for baseline fibrinogen (variable “_b_fibrinogen”, categorized into four classes (\leq 2 g/L,]2;3] g/L,]3,4] g/L, $>$ 4 g/L) and centre (see SAS code in §7.1). Missing data will be not imputed, assuming the missing completely at random (MCAR) assumption.

The treatment effect (odds ratio of failure) with its 95% confidence interval (95% CIs) will be provided by treatment group and tested at the 5% two-sided level of significance in this model.

Validity of the primary analysis: A graphical analysis of residuals will be done for verifying that assumptions for the primary analysis are met. If adjusting for centre effects lead to convergence issues or unstable estimates, centre effect will be ignored in the analysis.

3.3.6.2.3 *Sensitivity Analyses of the primary endpoint*

3.3.6.2.3.1 Primary sensitivity analysis (MAR assumption)

Assuming the missing at random (MAR) mechanism, multiple imputation (MI) approach by Fully Conditional Specification (FCS) will be used to handle missing data of the primary efficacy endpoint.

A stepwise logistic regression will be done to identify relevant covariates by a backward elimination analysis based on iterative maximum likelihood with the Newton-Raphson algorithm using a significance level of 0.2 to retain variables in the model. Only relevant covariates will be introduced in the MI process. The number of imputations needed will be verified with relative efficiency (RE) for the fully efficient imputation (in unit of variance) and by replicating sets of imputations checking whether the estimates are stable between imputation sets. With a little of missing information (10%), only a small number of imputations are necessary.

The final set of key covariates (referenced here below in the SAS syntax as “key_covariates_for_MI”, see §7.2 for SAS code) to be accounted for in the MI model in addition to treatment and categorized baseline fibrinogen will be defined before breaking the blind.

3.3.6.2.3.2 Secondary sensitivity analysis (MNAR assumption)

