All missing data for the primary endpoint will be estimated as failures assuming a missing not at random (MNAR) mechanism. The same model as the one proposed for the primary analysis will be fitted on the new data set considering missing data as failures.

3.3.6.2.3.3 Per Protocol analyses

Same primary model analyses will also be performed in the PP set assuming the MAR, MCAR and MNAR assumptions to handle missing data of the primary efficacy endpoint.

3.3.6.2.4 *Other efficacy analyses of the primary endpoint*

- *Analysis of the baseline fibrinogen as continuous:*

A logistic model will be fitted adjusting linear and quadratic effects of baseline fibrinogen.

- *Analysis of the centre and baseline fibrinogene interactions with treatment:*

Treatment by center and treatment by categorized baseline fibrinogen interactions will be investigated in a logistic regression adjusting for baseline fibrinogen, centre and interactions (see §7.3 for SAS code).

Odds ratios with their 95%CIs will be provided by centre and treatment group and illustrated in forest plots.

3.3.6.2.5 *Individual component analyses of the primary endpoint*

The analysis of the contribution of each component of the composite primary endpoint will be considered as descriptive analyses. Odds ratios and 95%CIs will be provided.

3.3.6.2.5.1 Administration of RBCs from H0 to D2

The percentage of patients requiring the transfusion of at least 2 units of RBCs within 48 hours following IMP administration will be calculated and logistic regression adjusting for baseline fibrinogen value (categorized) will be used to compare the Clottafact[®] group and placebo group.

The same subgroup analyses planned for the primary endpoint will be performed as well.

3.3.6.2.5.2 Percentage of patients losing at least 4g/dL of haemoglobin from H0 to D2

The percentage of patients losing at least 4 g/dL of haemoglobin within 48 hours following IMP administration with regards to the haemoglobin reference level will be calculated. A logistic regression adjusting for baseline fibrinogen value (categorized) will be used to compare the Clottafact[®] group and placebo group.

The same subgroup analyses planned for the primary endpoint will be performed as well.

3.3.6.2.6 *Subset analyses*

Subset analyses will be performed to estimate the percentage of failure by treatment group and by baseline covariates level in ITT and PP sets.

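### Dosed women with a known primary endpoint but no fibrinogen value before IMP start drop out of the primary and missing-as-failure analyses, because the four-class covariate has no level for them

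*SAP*

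**What the plan says.** SAP 3.3.6.2.2 defines the primary analysis as a logistic regression on treatment, centre and baseline fibrinogen, the last "categorized into four classes" (up to 2, above 2 to 3, above 3 to 4, and above 4 g/L). The code in SAP 7.1 is "model _resp = _trt centre _b_fibrinogen /influence iplots". Its CLASS statement names a reference level for fibrinogen but carries no MISSING option.

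SAP 3.3.5.3, like Protocol 12.8.3, fixes the timing: "Baseline data are defined as the last available data before the start of IMP infusion". Protocol 8.2.1 and the flow chart (Table 1) schedule one fibrinogen sample before that point, at inclusion. On the infusion itself, Protocol 8.2.2 says: "The start of IMP infusion corresponds to H0 and should be within the 30 minutes following the start of prostaglandins infusion". Protocol 5.2 does not make a fibrinogen result a condition of entry.

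On missing data, SAP 3.3.3 gives a general rule of no replacement, and SAP 3.3.6.2.2 adds for the primary model: "Missing data will be not imputed, assuming the missing completely at random (MCAR) assumption". The specific provisions (a substitute Hb value, committee confirmation, MI, missing counted as failure) all concern the endpoint. For the missing-as-failure analysis, SAP 3.3.6.2.3.2 says: "The same model as the one proposed for the primary analysis will be fitted on the new data set considering missing data as failures". SAP 3.3.6.2.1 places the primary analysis on the ITT set, and SAP 3.3.3 wants the analysed population to stay near the full randomised set.

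**The concern.** The gap concerns the covariate, not the outcome. A woman can be randomised, dosed and fully assessed for the primary endpoint, yet have no fibrinogen result from before the infusion. The sample is taken after emergency consent, during active bleeding, and is analysed locally (Protocol 8.3). The infusion follows within half an hour of starting prostaglandins. The trial's rationale (Protocol 1.3.1) is to avoid the delay of waiting for a fibrinogen result, so nothing in the pathway stops treatment when a sample is absent or late.

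If such women are deleted, the primary result rests on a subset of the ITT set that the SAP never defines. Counting missing endpoints as failures does not bring them back, because the same model is refitted. The component models in SAP 3.3.6.2.5 also adjust for categorised fibrinogen and lose them too. The final power statement in SAP 1.11 makes no allowance for this loss.

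**Working it through.** **Step 1. Who is deleted.** PROC LOGISTIC by default drops any record with a missing explanatory variable. The four classes cover every numeric value and no missing one. With no replacement and no MISSING option, a record without a pre-IMP fibrinogen value is dropped whatever is known about its endpoint. The same follows for the missing-as-failure analysis.

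**Step 2. The MI analysis.** SAP 3.3.6.2.3.1 uses MI for the endpoint. The code in SAP 7.2 lists a fibrinogen variable in VAR and CLASS, printed with a trailing underscore. The FCS and model statements print it without one (possibly a typing or PDF artefact). The only FCS method named is for the response. Whether a missing fibrinogen class would be imputed, and how, cannot be determined from this.

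**Step 3. Reproduce the plan's figures.** With an unpooled Z test, two-sided 5% and 90% power:

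n per arm = (1.960 + 1.282)² × [p1(1−p1) + p2(1−p2)] / (p1−p2)²

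- 42% v 27%: 10.507 × (0.2436 + 0.1971) / 0.0225 = 205.8, so 206, as stated. 206/0.95 gives 217 per arm, 434 in all, as stated.
- The blinded overall failure rate behind the revised size of 470 is not given. On a half-point grid, 42.5% (50% v 35%) reproduces it: 10.507 × (0.2500 + 0.2275) / 0.0225 = 223.0; divided by 0.95 this gives 235 per arm, 470 in all. I take this rate as an assumption.
- Women dosed: 448 × (1 − 0.0155) = 441. Power = Φ(0.15/√(0.4775/220.5) − 1.960) = Φ(1.264) = 89.7%, against 89.6% stated.

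The loss the SAP counted is "assuming that 1.55% of patients excluded from the ITT analysis (i.e. patients without receiving at least a dose of the IMP"), and no other.

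**Step 4. Apply the deletion.** Let m be the share of the 441 with no usable baseline fibrinogen. The documents do not give m. With n per arm = 441.06 × (1−m)/2:

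| m (assumed) | Women lost | Women analysed | Power |
|---|---|---|---|
| 0% | 0 | 441 | 89.7% |
| 2% | 9 | 432 | 89.1% |
| 5% | 22 | 419 | 88.1% |
| 10% | 44 | 397 | 86.4% |

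**Step 5. Dependence on the assumed rate.** For m of 0, 2, 5 and 10%, an overall failure rate of 40% gives 90.2, 89.6, 88.7 and 87.0%; a rate of 50% gives 89.0, 88.4, 87.4 and 85.6%. The fall is much the same: 3.2 to 3.4 points at 10% missing.

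These figures use the plan's unadjusted Z test as a guide; the analysis itself is an adjusted logistic regression.

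**The case against.** Several counter-arguments have force.

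- **The SAP is not silent.** Its no-replacement rule is general, so complete-case handling is the default. This stands: a reader might infer that no rule applies at all, and that would be wrong. But the rule's consequence for this covariate is not discussed, and it works against the ITT aim.
- **Bias between arms is not shown.** A reader might infer that the fastest bleeders are lost and the comparison distorted. The documents give no figure on who lacks a sample. Sampling precedes a blinded infusion, so its absence should not depend on arm. This stands.
- **The MI analysis need not use different women.** A reader might conclude from the VAR list that it does, and that the sensitivity analyses cannot be read. Given step 2, the documents support only that the handling is undefined.
- **A late study sample does not by itself exclude a woman.** An earlier pre-IMP value would serve, and only the draw, not the result, must come first. This stands, though only one such sample is scheduled.
- **Other outputs keep these women.** The raw failure percentages (SAP 3.3.6.1.2) need no fibrinogen value, nor do the section 7.4 models for covariates other than fibrinogen. True, but none of these is the primary test.
- **The 5% drop-out allowance absorbs the loss.** At 470 recruited, 1.55% plus 2% would fit. At 448 it does not: 2 × 223 = 446 evaluable women were needed, and the 441 dosed are already fewer. It is fair to add that the 89.6% makes no deduction for missing endpoints either.
- **The code is a fragment.** The derivations of `_b_fibrinogen` and of the analysis data set are not shown. If a missing level exists there, the text should say so, because it lists four classes.

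**Conclusion.** The point holds as a specification gap with a modest, quantifiable cost. As written, a dosed woman with a known endpoint and no pre-IMP fibrinogen value leaves the primary and missing-as-failure analyses, so the primary result is not on the full ITT set. The loss of power is about half a point at 2% missing, about 1.5 points at 5% and about 3.3 points at 10%. This rests on an assumed missing rate, an overall failure rate of 42.5% inferred from the revised sample size, and default software handling of a missing class value. The finding is one of precision and completeness; the documents do not support a claim of bias between arms. It is still worth correcting, because the analysis can keep these women at almost no cost, and settling the matter before unblinding avoids a later choice about who counts in the primary result.

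**What to change.** Before unblinding:

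1. State in SAP 3.3.6.1.2 and 3.3.6.2.2, and in the code of 7.1 and 7.2, that women with no pre-IMP fibrinogen value enter a separate missing class. Use the same variable in the primary, MI, missing-as-failure, per-protocol and component models. The covariate is then complete, so MI deals with the endpoint alone, as its text intends. Make the variable name consistent in 7.2.
2. Fix in advance, blind to arm, a minimum size for that class, and name one arm-blind imputation to use if the class falls below it.
3. Report the number of women affected, by arm.
4. Leave the interaction model in 7.3 on the four observed classes. It already crosses fibrinogen with centre and with treatment, and a fifth level would thin those cells further.

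The cost is a short addition to the SAP text and one class level in the code. The blinded data review in SAP 3.2 is a natural point at which to see the pooled count and close the rule.
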